9.3.3 Removal of Subjects From Therapy or Assessment

The investigator may discontinue treating a subject with study treatment or withdraw the subject from the study at any time for safety or administrative reasons. The subject may decide to discontinue study treatment or withdraw from the study at any time for any reason. The reason for discontinuation will be documented. After discontinuation from study treatment and completing off-treatment visit, subjects will be followed up at least 4 weeks later (ie, greater than or equal to 28 days after last dose but no more than 1 year) unless they withdraw consent. The investigator should confirm whether a subject will withdraw from study treatment but agree to continue protocol-specified, off-treatment study visits, procedures or whether the subject will withdraw consent. If a subject withdraws consent, the date will be documented in the source documents. The Discontinuation From Treatment CRF page will be completed indicating the primary reason(s) for discontinuation. In addition, the date of last dose of study drug(s) will be recorded on the Study Drug Dosing CRF page. Before a subject is withdrawn from study medication due to AE, the possibility of continuing on a single agent should be considered. In the event of an adverse event which leads to treatment interruption or delay of either study drug. The subject may continue treatment with the other study drug as long as there is a clinical benefit for up to 1 year, from start of study treatment, after which any continued treatment would need to be discussed with the Sponsor.

During the Follow-Up Period, subjects who have discontinued study treatment without objective disease progression should have tumor assessments performed according to the

Schedule of Assessments from the date of the last assessment until disease progression is documented or another anticancer therapy is initiated, whichever occurs first, unless the study is terminated or the subject withdraws consent for follow-up.

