Criteria for Dosing Modifications

Dose reduction and interruption for eribulin mesilate and irinotecan hydrochloride-related toxicity will be performed according to the following instructions:

Treatment will not be administered if any of the following values are recorded ([Table 7](#)).

Table 7 Criteria for Administration of Study Medication	
a): Do not administer Cycle 1 Day 1 treatment where:	
Absolute Neutrophil Count	<1.0 × 10 ⁹ /L or 1,000/mm ³
Platelets	<100 × 10 ⁹ /L or 100,000/mm ³
Non-hematological toxicity	Any >Grade 2 except for inadequately treated nausea and/or vomiting.
Gastrointestinal toxicity	Bowel function deteriorated since pre-treatment/baseline and requires antidiarrheal medications for within 24 hours before the next chemotherapy administration.
b): Do not administer any Day 8 treatment where:	
Absolute Neutrophil Count	<0.75 × 10 ⁹ /L or 750/mm ³
Platelets	<75 × 10 ⁹ /L or 75,000/mm ³
Non-hematological toxicity	Any >Grade 2 except for inadequately treated nausea and/or vomiting.
Gastrointestinal toxicity	Bowel function deteriorated since pre-treatment/baseline and requires antidiarrheal

	medications for within 24 hours before the next administration of irinotecan hydrochloride.
c): Do not administer any subsequent Day 1 treatment where:	
Absolute Neutrophil Count	$<1.0 \times 10^9/L$ or $1,000/mm^3$
Platelets	$<75 \times 10^9/L$ or $75,000/mm^3$
Non-hematological toxicity	Any >Grade 2 except for inadequately treated nausea and/or vomiting.
Gastrointestinal toxicity	Bowel function deteriorated since pre-treatment/baseline and requires antidiarrheal medications for within 24 hours before the next chemotherapy administration.

If the dose cannot be administered as planned due to treatment-related toxicity, the dose should be delayed according to the following instructions.

Day 1 of each cycle: If treatment cannot be administered on Day 1, the dosing should be delayed until recovery to above these values ([Table 7a](#) Cycle 1 & c subsequent cycles). The Day 1 dose will be rescheduled for when the criteria for treatment administration are met. The dose level may have to be reduced following a dose delay in accordance to the instructions for dose reduction ([Table 8](#)).

Day 8 of each cycle: If treatment cannot be administered on Day 8, the dosing should be delayed until recovery to above these values ([Table 7b](#)) as follows:

Hematological toxicity:

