- Subjects who have Grade 4 neutropenia or platelets $<75,000/mm^3$ on Day 8 will have their dose withheld. If the toxicity resolves to ANC $\geq 750/mm^3$ and platelets $\geq 75,000/mm^3$ (transfusion independent) by Day 11, the dose may be given. If the toxicity does not resolve to ANC $\geq 750/mm^3$ and platelets $\geq 75,000/mm^3$ by Day 11, the dose will be omitted and this will be considered a DLT. Subjects should receive subsequent cycles of drug but at the next lower dose level ([Table 10](#)). Subjects who require that their Day 8 dose be omitted for Grade 4 neutropenia or platelets $<75,000/mm^3$ after two dose reductions must be removed from protocol therapy.
- Subjects who meet hematological DLT criteria on Day 8 will have their Day 8 dose omitted. Subjects should receive subsequent cycles of drug but at the next lower dose level. Subjects who require that their Day 8 dose be omitted for hematologic DLT after two dose reductions must be removed from protocol therapy.

Non-hematological toxicity:

- Subjects who have Grade 3 or Grade 4 non-hematological toxicity attributable to the study drug prior to the Day 8 dose (with the exception of the DLT exclusions) will be

considered to have had a DLT. If the toxicity resolves to meet eligibility or \leq Grade 2 (if not part of eligibility criteria) by Day 8, the dose may be given but at the next lower dose level.

- Subjects who have Grade 3 or Grade 4 non-hematological toxicity attributable to the study drug on Day 8 prior to dosing (with the exception of the DLT exclusions) will have their dose withheld and this will be considered a DLT. If the toxicity resolves to meet eligibility or \leq Grade 2 (if not part of eligibility criteria) by Day 11, the dose may be given but at the next lower dose level. If the toxicity does not resolve by Day 11, the dose will be omitted. Subjects should receive subsequent cycles of drug but with dose modifications ([Table 10](#)).
- For subjects <12 months any \geq Grade 2 non-hematological toxicity attributable to study drug prior to the Day 8 dose will have their dose omitted. Subjects should receive subsequent cycles of drug at the next lower dose level ([Table 10](#)).
- Subjects who have a dose-limiting hematological or non-hematological toxicity that does not resolve to meet eligibility or baseline parameters within 21 days after the planned start of the next treatment cycle must be removed from protocol therapy.

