For Schedule A, irinotecan doses days 2-5 can be delayed up to cycle Day 10 (of a 21 day cycle), at the discretion of the Investigator and as long as the subject meets the criteria for administration of study medication for Day 8 as detailed in [Table 7](#). If the subject does not meet the Day 8 criteria for administration by cycle Day 10 then dosing should not occur until the next cycle and as long as the subject meets the subsequent Day 1 dosing criteria for administration ([Table 8](#)).

Please note, use of hematopoietic growth factor support is not permitted in Cycle 1 and is only permitted in subsequent cycles as per institutional guidelines. Subjects known to have reduced UGT1A1 activity will be monitored carefully for hematological toxicity.

The treatment will be permanently reduced to the next lowest dose level ([Table 10](#)) after the occurrence of the following events

Table 8 Criteria for Reduction of Study Medication to the Next Lowest Dose Level

Absolute Neutrophil Count	Grade 4 neutropenia >7 days Grade 3 or 4 febrile neutropenia and/or infection requiring treatment with antibiotics and/or growth factors
----------------------------------	---

Platelets	Grade 4 thrombocytopenia Grade 3 thrombocytopenia requiring platelet or blood transfusion or both
Non-hematological toxicity	Grade 3 or 4 toxicities (attributable to study drug); except Grade 3 hypophosphatemia, hypokalemia, hypocalcemia or hypomagnesemia that respond to supplementation For subjects <12 months any \geq Grade 2 non-hematological toxicity attributable to study drug prior to the Day 8 dose will have their dose omitted and this will be considered a DLT. Subjects should receive subsequent cycles of drug but with dose modifications as per Table 10
Gastrointestinal toxicity	\geq Grade 3 or intolerable Grade 2 diarrhea For subjects on dose levels 0 and -1 dose reductions of 20% of the current irinotecan dose should be made. If there are 2 or more diarrhea DLTs on these dose levels, the irinotecan dose levels will be re-evaluated by the Sponsor, and an appropriate lower dose level will be agreed with the investigator. If the diarrhea toxicity does not recover following a dose reduction of 20% (of dose level 0 or -1), treatment should be discontinued

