If hematological or non-hematological toxicities do not recover following a dose reduction to dose level -1 (dose-level -2 for subjects <12 months) and the use of hematopoietic growth factors, for hematological toxicities, the subject will discontinue treatment (except for cases of irinotecan related diarrhea, see below). However, if the subject is deemed to have clinical benefit, continuation of treatment may be discussed with the sponsor.

To ensure safety for subjects, the study drug must be discontinued in the cases outlined in [Table 9](#).

If, in the opinion of the Investigator, a dose reduction as per the criteria noted in [Table 8](#) is not necessary, due to adequate supportive care and use of prophylaxis (eg, growth factor support) to prevent recurrences, each individual case should be discussed with and agreed by the Sponsor.

Table 9 Criteria for Discontinuation of Study Medication

ALT $>3 \times$ ULN and total bilirubin $>2 \times$ ULN

ALT >8 × ULN at any time, regardless of total bilirubin or accompanying symptoms
ALT >5 × ULN for 2 or more weeks, regardless of total bilirubin or accompanying symptoms
ALT >3 × ULN, accompanied by symptoms consistent with hepatic injury (fatigue, nausea, vomiting, right upper quadrant pain or tenderness, fever, or rash). Clinical judgement should be used based on the combination of the laboratory LFT results and clinical symptoms. Additionally, in subjects with liver metastases with pre-existing ALT >3 x ULN at study baseline, any additional increase in ALT values from baseline and clinical symptoms consistent with a syndrome of hepatic injury as described above should be considered for further assessment and drug discontinuation. Clinical symptoms alone consistent with deterioration of liver function should lead to additional laboratory assessments and evaluation of potential study drug related liver toxicity.

Instructions for QTc prolongation on electrocardiogram (ECG):

Increase the frequency of ECG and electrolyte monitoring in subjects who: develop Grade 2 QTc prolongation, are receiving agents that are known to prolong QTc interval, or have clinically relevant electrolyte abnormalities. Permanently discontinue study treatment in subjects who develop \geq Grade 3 QTc prolongation, and monitor ECGs and electrolytes more frequently in consultation with cardiologist advice and in line with local practice until the QTc interval returns to baseline.

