Table 10 Study Medication Dose Levels by Schedule for Phase 1

Dose Level	Eribulin mesilate (mg/m ²)	Irinotecan hydrochloride (mg/m ²)
Schedule A		
-2	0.8	20
-1	1.1	20
0	1.4	20
1	1.4	40
Schedule B		
-1	1.1	100
0	1.4	100
1	1.4	125

Dose level -2 is a further dose reduction in Schedule A for subjects <12 months only.

Do not re-escalate dose level after the dose level has been reduced.

Phase 2

As per protocol amendment #5, the data from the Phase 1 portion of this study showed that there was a tolerable safety profile in both schedules, with similar PK profiles; however, 2 PRs were noted in Schedule A, one of which was confirmed. Following discussions with the investigators and independent experts, based upon the similar toxicity and PK profiles and taking into account the 2 PRs noted in Schedule A, Schedule A Dose Level 1 (eribulin 1.4

mg/m² D1 and D8 with irinotecan 40 mg/m² D1 – D5 of a 21- day cycle) from Phase 1 was selected as the RP2D for the Phase 2 portion of this study for subjects \geq 12 months of age.

As per Amendment 6, subjects aged >6 months and <12 months will be enrolled to Schedule A with a modified dose of eribulin Dose Level -2 (0.8 mg/m² D1 and D8) with the irinotecan dose maintained Dose Level 1 (40 mg/m² D1 – D5) of a 21-day cycle.

A modified dose of eribulin with the irinotecan dose maintained is being used for subjects <12 months in order to maximize safety for infant subjects. The modified dose of eribulin is aligned with the Children's Cancer and Leukaemia Group ([CCLG](#)) ([Chemotherapy Standardization Group 2008](#)) guidance on pediatric dosing where a dose has not been established.

The dose levels as per [Table 11](#) should be used in the Phase 2 portion of the study when following the criteria for dose reductions ([Table 8](#)), the agent most likely to be the cause of toxicity (eg, irinotecan for diarrhea, eribulin for neuropathy or neutropenia) should be reduced by one dose level if these criteria are met. If in the investigator's opinion both agents should be reduced this may be permitted after discussion with the Sponsor.

Table 11 Schedule A Dose Levels for Phase 2	
Dose Level	Eribulin mesilate (mg/m²)
Eribulin – Days 1 & 8	
-4	0.4
-3	0.6
-2**	0.8
-1	1.1
1*	1.4
Irinotecan hydrochloride (mg/m²) – Days 1-5	
-2	20
-1	30
1*	40

For subjects \geq 12 month to \leq 25 years of age:

* Dose level 1 eribulin (1.4 mg/m² Days 1 and 8) and irinotecan (40 mg/m² Days 1 – 5).

For subjects >6 months and <12 months of age:

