**Dose level -2 for eribulin (0.8 mg/m² Days 1 and 8) and Dose level 1 for irinotecan (40 mg/m² Days 1 – 5) is maintained.

[figure not shown]
Do not re-escalate dose level after the dose level has been reduced. If toxicities do not recover after 2 dose reductions, treatment with that agent must be discontinued.

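### Phase 2 dose-modification text keeps Phase 1 level labels that do not fit Table 11, leaving two discontinuation rules and two irinotecan steps for diarrhoea; separately, the infant eribulin dose put at about 75% of the RP2D is 57%

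*Protocol*

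**What the plan says.** The block on dose modification in Protocol Section 9.4.1 opens without a phase limit: "Dose reduction and interruption for eribulin mesilate and irinotecan hydrochloride-related toxicity will be performed according to the following instructions". The relevant statements are these.

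- **General discontinuation sentence** (below Table 8; Synopsis, below Table 2). The trigger is "If hematological or non-hematological toxicities do not recover following a dose reduction to dose level -1 (dose-level -2 for subjects <12 months", together with growth factor use for haematological toxicity. The subject then stops treatment. Irinotecan-related diarrhoea is excepted. The sentence is softened by "However, if the subject is deemed to have clinical benefit, continuation of treatment may be discussed with the sponsor".
- **Phase 2 discontinuation sentence** (below Table 11; Synopsis, below Table 5). "If toxicities do not recover after 2 dose reductions, treatment with that agent must be discontinued".
- **Day 8 haematological rule.** Subjects who need the Day 8 dose omitted "after two dose reductions must be removed from protocol therapy".
- **Section 9.3.3.** "Before a subject is withdrawn from study medication due to AE, the possibility of continuing on a single agent should be considered".
- **Link between the tables.** Table 11 levels "should be used in the Phase 2 portion of the study when following the criteria for dose reductions", meaning Table 8. The agent most likely responsible comes down one level, and irinotecan for diarrhoea is one of the examples.
- **Table 8, diarrhoea row.** "For subjects on dose levels 0 and -1 dose reductions of 20% of the current irinotecan dose should be made". If the 20% cut fails, treatment stops.
- **Table 8, infant row.** It points to Table 10, the Phase 1 ladder, for the modified dose.
- **Infant dose.** Section 9.7.2 and the Synopsis (Statistical Methods) give about 75% of the eribulin RP2D for infants aged over 6 and under 12 months. This is the reason for leaving them out of the full sample size analyses. The doses in Section 9.4.4 are 0.8 mg/m² for infants and 1.4 mg/m² for the RP2D.

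**The concern.** Level labels in the general block match the Phase 1 ladder (Table 10). The Phase 2 ladder (Table 11) reuses the labels with different meanings: it has no level 0, its irinotecan level -1 is 30 rather than 20 mg/m², and it numbers each agent separately. Read with Table 11, the same sentences give different instructions from the Phase 2 text beside them.

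These are working reduction and stopping rules for children, used at up to about 50 sites. Two sites, each following the protocol, could stop treatment at different points, stop both drugs or only one, or give different irinotecan doses for the same event. The sponsor-discussion clause narrows the gap only when clinical benefit is judged present.

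The percentage is a separate matter. It misstates the infant dose relative to the RP2D in the very sentence that justifies an analysis exclusion.

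**Working it through.** **Inputs (mg/m²)**

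| Level | Table 10, Schedule A: eribulin / irinotecan | Table 11: eribulin | Table 11: irinotecan |
|---|---|---|---|
| 1 | 1.4 / 40 | 1.4 | 40 |
| 0 | 1.4 / 20 | none | none |
| -1 | 1.1 / 20 | 1.1 | 30 |
| -2 | 0.8 / 20 (infants only) | 0.8 (infant start) | 20 |
| -3 | none | 0.6 | none |
| -4 | none | 0.4 | none |

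Phase 2 infants start at eribulin 0.8 and irinotecan 40.

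**1. Reductions before discontinuation, subjects aged 12 months or more**

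- General sentence on Table 11: level 1 to -1 is 1 reduction (eribulin 1.4 to 1.1, or irinotecan 40 to 30).
- Phase 2 sentence: 2 reductions (eribulin to 0.8, or irinotecan to 20).
- General sentence on Table 10: 1 to 0 to -1 is 2 steps, so the count agrees.

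On either ladder two differences remain. The general sentence stops the subject's treatment, while the Phase 2 sentence stops one agent. Only the general sentence allows continuation to be discussed with the sponsor. The Day 8 rule also counts two reductions but removes the subject, and Section 9.3.3 asks that a single agent be considered first.

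**2. Infants**

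The general sentence needs a reduction to level -2. In Phase 2 that is the infant eribulin starting level, so no such reduction can occur. The Phase 2 sentence with Table 11 allows 0.8 to 0.6 to 0.4. Table 8's infant row points to Table 10, which has no eribulin level below 0.8 and pairs 0.8 with irinotecan 20, not the 40 at which Phase 2 infants start.

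**3. Diarrhoea**

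- At irinotecan level 1 there is no conflict. The 20% row names only levels 0 and -1, so the Table 11 step applies: 40 to 30, a cut of 10/40 = 25%.
- At level -1 under Table 8: 30 × 0.8 = 24 mg/m², or 24 × 5 = 120 mg/m² per cycle. Treatment stops if this fails.
- At level -1 under Table 11: 20 mg/m², or 20 × 5 = 100 mg/m² per cycle, a cut of 10/30 = 33.3%.

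**4. Infant percentage**

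- Stated: about 75% of the RP2D.
- From the doses: 0.8/1.4 = 57.1%. Dosing days are the same, so the weekly ratio is also 57.1%.
- 75% of 1.4 would be 1.05 mg/m² (arithmetic only). The gap is 75 - 57.1 = 17.9 points.
- Allowing for rounding of both doses: 0.75/1.45 = 51.7% to 0.85/1.35 = 63.0%.
- The nearest match is 0.8/1.1 = 72.7%, but that is against level -1, not the RP2D.

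The stated figure cannot be reproduced against the RP2D.

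**The case against.** The best reply is that the general block is Phase 1 text. In Section 9.4.1 it falls between a Phase 1 and a Phase 2 heading, it points to Table 10, and on Table 10 the reduction counts agree. The diarrhoea row also makes sense there: Schedule A levels 0, -1 and -2 all carry irinotecan 20, so stepping down a level would not lower irinotecan. The Phase 2 text names irinotecan for diarrhoea and says to use Table 11, which could be taken to displace both the 20% row and the pointer to Table 10. An infant limit that cannot operate in Phase 2 is further evidence of Phase 1 origin.

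That is probably how the text arose, but it does not settle how it reads:

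- In the Synopsis the same block comes after a Phase 2 subheading, so placement cannot confine it to Phase 1.
- The Phase 2 text brings in the Table 8 criteria without excluding any row.
- The block holds the study's only criteria for giving a dose (Table 7), its hepatic stopping criteria (Table 9) and its QTc stopping rule. If it were Phase 1 only, Phase 2 would have none of them.
- Section 9.5.1.4.3 sends readers to Tables 8 and 9 for laboratory abnormalities without a phase limit.

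Other parts of the reply stand. The Day 8 rule has its own trigger, and Section 9.3.3 is compatible with stopping one agent. They need aligning with the rest but are not the core conflict. Section 9.4.4 ties 75% to outside guidance on the calculated dose and gives reasons for choosing level -2. That explains where the figure came from, but Section 9.7.2 and the Synopsis state it as a share of the RP2D. The 57.1% is a dose ratio and says nothing by itself about drug exposure in infants.

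**Conclusion.** The concern holds, and the text must be fixed.

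- **Discontinuation.** For subjects aged 12 months or more in Phase 2, the two rules differ by one reduction if level -1 is read on Table 11. On any reading they differ in scope (subject or agent) and in the sponsor exception. For infants, the general rule's eribulin limit has no effect in Phase 2.
- **Diarrhoea.** The conflict is confined to irinotecan level -1: 24 or 20 mg/m² per day, 120 or 100 mg/m² per cycle.
- **Infant dose.** It is 57.1% of the eribulin RP2D, not about 75%.

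The one-reduction gap depends on the Table 11 reading, which the protocol neither requires nor rules out. The infant dose is 0.8 mg/m² wherever it is stated, infants are excluded from the full sample size analyses at either percentage, and no Simon design figure changes. This is a matter of consistent treatment and safety rules, not of the primary test.

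**What to change.** Amend Section 9.4.1 from the Day 8 rules through Table 11, and the matching Synopsis text with Tables 2, 4 and 5, so that:

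- each Phase 2 age group has one reduction ladder and one discontinuation rule;
- that rule says whether it stops the agent or the subject, and whether sponsor discussion for clinical benefit applies;
- any Phase 1-only wording is labelled, including the general discontinuation sentence and Table 8's diarrhoea and infant rows if that is what is meant;
- the Day 8 removal rule and the single-agent sentence in Section 9.3.3 agree with the result.

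Reconcile the percentage in Section 9.7.2 and the Synopsis with the stated 0.8 and 1.4 mg/m². Which rule or dose applies is for the sponsor and its clinical experts to decide.

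The cost is amendment wording: no extra subjects or procedures, and no change to the sample size or analysis.

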9.4.2 Identity of Investigational Products

Eribulin mesilate will be supplied by the sponsor in labeled vials. Irinotecan hydrochloride will either be supplied by sponsor or sourced locally by the investigator site, depending on local requirements.

[figure not shown]
